PHILIP MORRIS PRODUCTS S.A.

Clinical Study Protocol

Study Number:	P5-PK-01-EXP
Study Title:	A single-center, randomized, controlled, open-label study to investigate the nicotine pharmacokinetic profiles and subjective effects of four variants of Nicotine pouch 1.0 compared to Velo® Ice Cool and Zyn® Cool Mint Mini Dry in healthy smokers
Short title:	Nicotine pharmacokinetics and subjective effects of Nicotine pouch 1.0 nicotine pouches compared to Velo® Ice Cool and Zyn® Cool Mint Mini Dry in healthy smokers
Product Name:	Nicotine pouch 1.0
Sponsor:	Philip Morris Products S.A. [name]
Version:	2.0,
Date:	Approved 07 Mar 2022
Authors:	, PhD, Clinical Scientist PhD, Biostatistician , MD, Medical Safety Officer

Confidentiality Statement

Document ID: VV-TMF-00821

VERSION HISTORY

Version	Date	Protocol Update/Amendment
2.0	07 Mar 2022	Amendment 1
Original Document 1.0	04 Feb 2022	Not applicable

SUMMARY OF CHANGES FROM PREVIOUS VERSION

• Appendix B: Safety laboratory amended

Confidentiality Statement

Clinical Study Protocol 2.0, Approved

Document ID: VV-TMF-00821

SYNOPSIS

Sponsor:

Philip Morris Products S.A. [name]

Name of Product:

Nicotine pouch 1.0

Study Title:

A single-center, randomized, controlled, open-label study to investigate the nicotine pharmacokinetic profiles and subjective effects of four variants of Nicotine pouch 1.0 compared to Velo® Ice Cool and Zyn® Cool Mint Mini Dry in healthy smokers

Study Number:

P5-PK-01-EXP

Short Title:

Nicotine pharmacokinetics and subjective effects of Nicotine pouch 1.0 nicotine pouches compared to Velo® Ice Cool and Zyn® Cool Mint Mini Dry in healthy smokers

Exploratory Objective and Endpoints:

1. To describe the plasma concentration-time profile of nicotine and derived pharmacokinetic (PK) parameters of 4 variants of Nicotine pouch 1.0 nicotine pouches compared to Velo-NP and Zyn-NP in healthy smokers from a 30 minutes product use period.

Endpoints (Day 1 to Day 3):

- Background-corrected maximum plasma concentration [C_{max}]
- Background-corrected time to the maximum concentration [T_{max}]
- Area under the background-corrected concentration-time curve (AUC) from start of product use (T₀), to all subsequent timepoints and extrapolated to infinity [AUC_{0-5min}, AUC_{0-10min}, AUC_{0-15min}, AUC_{0-20min}, AUC_{0-25min}, AUC_{0-30min}, AUC_{0-35min}, AUC_{0-40min}, AUC_{0-1h}, AUC_{0-3h}, AUC_{0-6h}, AUC_{0-infinity}]

Confidentiality Statement

Philip Morris Products S.A.	Clinical Study Protocol	Confidential
P5-PK-01-EXP	2.0, Approved	Page 4 of 98

2. To describe pharmacodynamic (PD) effects (subjective effects and related behavioral assessments) of 4 variants of Nicotine pouch 1.0 compared to Velo-NP and Zyn-NP in healthy smokers from a 30 minutes product use period.

Endpoints (Day 1 to Day 3):

- Score of cigarette craving by the visual analog sale (VAS)-craving assessment [VAS-C-15min, VAS-C5min, VAS-C10min, VAS-C15min, VAS-C20min, VAS-C25min, VAS-C30min, VAS-C35min, VAS-C40min, VAS-C1h, VAS-C3h, VAS-C6h]
- Score of "in the moment" product liking by the VAS-liking assessment [VAS-L_{5min}, VAS-L_{10min}, VAS-L_{15min}, VAS-L_{20min}, VAS-L_{25min}, VAS-L_{30min}, VAS-L_{35min}, VAS-L_{40min}, VAS-L_{1h}]
- Score of overall product liking by the VAS-liking assessment
- Score of product satisfaction by the VAS- satisfaction assessment [VAS-S_{5min}, VAS-S_{10min}, VAS-S_{15min}, VAS-S_{20min}, VAS-S_{25min}, VAS-S_{30min}, VAS-S_{35min}, VAS-S_{40min}, VAS-S_{1h}, VAS-S_{3h}, VAS-S_{6h}]
- Score of product intention to use again by the VAS-intention to use again assessment [VAS-ITU_{30min}, VAS-ITU_{3h}]
- Subscale scores from the Product Evaluation Scale (PES)
- Scores from items of the Sensory questionnaire
- 3. To evaluate the safety and tolerability during the study

Endpoints (from Enrollment to EOS):

- Incidence of adverse events (AEs) and serious adverse events (SAEs)
- Incidence of product events
- Changes in electrocardiogram (ECG) from baseline (heart rate, PR, QRS, QT, QTcF interval)
- Changes in vital signs from baseline (systolic and diastolic blood pressure, pulse rate and respiratory rate)
- Concomitant medication
- Changes from baseline in clinical chemistry, hematology, and urine analysis safety panel

Confidentiality Statement

Philip Morris Products S.A.	Clinical Study Protocol	Confidential
P5-PK-01-EXP	2.0, Approved	Page 5 of 98
P 1 (1) (0) (0 0017500		

4. To describe the associations between PK and PD parameters.

Endpoints (Day 1 to Day 3):

- Between the score of "in the moment" product liking by the VAS-liking assessment averaged over the product use period (from T1 to T6) and during the sequence period (T1 to T9) and C_{max}, T_{max}, and AUC_{0-infinity} PK endpoints
- Between the average score of "in the moment" product satisfaction by the VASproduct satisfaction assessment during the sequence's period (from T1 to T11) and C_{max}, T_{max}, and AUC_{0-infinity} PK endpoints
- Between the score of "in the moment" craving by the VAS-craving assessment averaged during the sequence's period (from T1 to T11) and C_{max} , T_{max} , and $AUC_{0-infinity}$ PK endpoints
- Between the subscale scores of Product Evaluation Scale and AUC_{0-infinity} PK endpoint
- Between the item scores of the Sensory questionnaire and AUC_{0-infinity} PK endpoint
- 5. To describe the extent of nicotine extracted during product use from 4 variants of Nicotine pouch 1, Velo-NP and Zyn-NP. Reporting of this objective will be separate from the main Clinical Study Report.

Endpoint (Day 1 to Day 3)

• Estimated amount of nicotine extracted derived from analysis of nicotine after use.

Study Design:

This is a single-center, randomized, controlled, open-label, cross-over study in healthy smoking subjects to investigate the nicotine PK profiles of 4 variants of Nicotine pouch 1.0 compared to marketed Velo-NP and Zyn-NP. In addition, PD effects will be evaluated to provide further insights on Nicotine pouch 1.0 product acceptance and abuse liability. The study will be conducted with 3 periods and 6 sequences in a Williams design (cross-over). The assessments to be performed will be as described in the schedule of events (Appendix A). The overall design will be as follows:

A Screening Visit will be conducted within 21 days (Day -22 to Day -2) prior to Admission (Day -1) to the investigational site (Figure 1). Subjects will be screened against eligibility criteria.

Confidentiality Statement

Document ID: VV-TMF-00821

Figure 1 Study Design

Qualified subjects will return to the investigational site for Day -1. Subjects should have fasted for at least 10 hours prior to the safety laboratory assessments. After confirmation of eligibility, subjects will be enrolled. All subjects that are not enrolled will be considered as screen failures.

At Day -1, enrolled subjects will perform a product test using NP-1 for 30 minutes (± 1 minute). After the product test, subjects not willing and/or not ready to use Nicotine pouch 1.0 during the study will be discontinued from the study, will enter the 3-day Safety follow-up period and will be replaced.

Subjects willing and ready to use Nicotine pouch 1.0, Velo-NP and Zyn-NP during the study after product test will start their exposure period of 3 days.

Twenty-four subjects will be randomized to 1 of 6 possible sequences of product use on Day 1 to Day 3 with at least 25% of each sex.

Confidentiality Statement

Philip Morris Products S.A.	Clinical Study Protocol	Confidential
P5-PK-01-EXP	2.0, Approved	Page 7 of 98

On Day 1 to Day 3, after at least 8 hours of abstinence from any nicotine/tobacco containing products (nicotine wash-out), subjects will use one nicotine pouch (NP) for 30 minutes (± 1 minute) according to randomized product use sequence in the morning and in the afternoon, by placing the NP between the upper lip and gum. Subjects will complete self-reported assessments of product evaluation, craving, liking, satisfaction, and intent to use again.

The start of the 30 minutes use period will be defined as T_0 . T_0 in the morning (T_{0M}) and in the afternoon (T_{0A}) on Day 1 to Day 3 should be approximately at the same time, within a window of \pm 30 minutes. Venous blood samples will be obtained according to the standard operating procedures (SOPs) at the investigational site.

On Day 1, 12 blood samples will be collected for determination of nicotine concentration at the following time points in relation to T0 with a time window as indicated in brackets:

Morning prior to T_{0M} and afternoon prior to T_{0A:}

• T-1: 5 minutes (± 1 minute)

After T_{0M} and T_{0A}

- T1 after 5 minutes (± 1 minute)
- T2 after 10 minutes (± 1 minute)
- T3 after 15 minutes (± 1 minute)
- T4 after 20 minutes (± 1 minute)
- T5 after 25 minutes (± 1 minute)
- T6 after 30 minutes (± 1 minute)
- T7 after 35 minutes (± 1 minute)
- T8 after 40 minutes (± 1 minute)
- T9 after 1 hour (\pm 5 minutes)
- T10 after 3 hours (\pm 5 minutes)
- T11 after 6 hours (± 5 minutes)

For each product use, subjective effects of liking, craving, satisfaction, and intention to use will be assessed at the following time points in relation to T0 with a time window as indicated in brackets:

Prior to T_{0M} and T_{0A} (for VAS craving only)

• T-15: within 15 minutes prior to T₀

Confidentiality Statement

Philip Morris Products S.A.	Clinical Study Protocol	Confidential
P5-PK-01-EXP	2.0, Approved	Page 8 of 98

After T_{0M} and $T_{0A:}$ (for VAS craving, VAS liking "in the moment", and VAS satisfaction "in the moment" assessments)

- T1 after 5 minutes (± 1 minute)
- T2 after 10 minutes (± 1 minute)
- T3 after 15 minutes (± 1 minute)
- T4 after 20 minutes (± 1 minute)
- T5 after 25 minutes (± 1 minute)
- T6 after 30 minutes (± 1 minute)
- T7 after 35 minutes (± 1 minute)
- T8 after 40 minutes (± 1 minute)
- T9 after 1 hour (\pm 5 minutes)
- T10 after 3 hours (± 5 minutes) (VAS craving and VAS satisfaction only)
- T11 after 6 hours (± 5 minutes) (VAS craving and VAS satisfaction only)

After T_{0M} and T_{0A}: (for VAS liking (overall) assessment)

• T10 after 3 hours (\pm 5 minutes)

After T_{0M} and T_{0A:} (for VAS intention-to-use again)

- T6 after 30 minutes (± 1 minute)
- T10 after 3 hours (\pm 5 minutes)

Additional subjective effects will be assessed in the morning and in the afternoon on Day 1 to Day 3 by the Product Evaluation Scale (PES) and the Sensory questionnaire administered at T9, 1 hour (\pm 5 minutes) after T_{0M} and T_{0A}.

Additional blood samples will be taken for determination of the nicotine concentration to evaluate terminal elimination half-life $(t_{1/2z})$ in relation to T_{0A} on Day 2 at the following time points with a time window as indicated in brackets:

- T1z after 8 hours (\pm 5 minutes) after T_{0A}
- T2z after 12 hours (\pm 5 minutes) after T_{0A}

After discharge at Day 3, the subjects will enter a 3-day Safety follow-up period during which AE/SAEs reported by the subjects associated with IP use will be collected and the follow-up of the ongoing AEs/SAEs will be conducted by the study investigational site.

Confidentiality Statement

Study Population and Main Criteria for Inclusion/Exclusion:

Subjects who meet all the following inclusion criteria will be enrolled into the study:

- 1. Subject has signed the ICF and is able to understand the information provided in the ICF.
- 2. Smoking male or female aged between 21 and 65 years inclusive.
- 3. Subject has smoked continuously for at least the last 3 years prior to the Screening visit.
- 4. Subject has smoked ≥ 10 commercially available cigarettes per day for 4 weeks prior to Screening Visit and Admission. Smoking status will be verified based on a urinary cotinine test (cotinine \geq 500 ng/mL).
- 5. Subject does not plan to quit using tobacco and/or nicotine products within the next 3 months.
- 6. Smoking, healthy subject as judged by the Investigator or designee based on available assessments from the Screening period (e.g., safety laboratory, spirometry, vital signs, physical examination, ECG and medical history).

Subjects who meet any of the following exclusion criteria must not be enrolled into the study:

- 1. As per the Investigator's judgment, the subject cannot participate in the study for any reason other than medical (e.g., psychological, social reason).
- 2. Subject is legally incompetent, or physically or mentally incapable of giving consent (e.g., emergency situation, under guardianship, prisoners).
- 3. Subject has a clinically relevant disease which requires medication (including but not limited to gastrointestinal, renal, hepatic, neurological, hematological, endocrine, oncological, urological, immunological, pulmonary, and cardiovascular disease) or any other medical condition including safety laboratory, which as per the judgment of the Investigator would jeopardize the safety of the subject.
- 4. As per the Investigator's judgment, the subject has medical conditions which require or will require in the course of the study, a medical intervention (e.g., start of treatment, surgery, hospitalization), which may interfere with the study participation and/or study results.
- 5. Subject has donated or received whole blood or blood products within 30 days prior to Screening Visit.
- 6. BMI < 18.5 kg/m2 or > 32.0 kg/m^2 .
- 7. Subject has received medication within 14 days or within 5 half-lives of the drug prior to Admission (whichever is longer), which has an impact on CYP2A6 activity.
- 8. Subject has a positive serology test for HIV 1/2, Hepatitis B or Hepatitis C.
- 9. Subject has a history of alcohol abuse, which as per the judgment of the Investigator could interfere with the subject's participation in study.
- 10. Subject has a positive urine drug including alcohol test.
- 11. Subject or one of their family members ^a is a current or former employee of the tobacco industry.

Confidentiality Statement

Philip Morris Products S.A.	Clinical Study Protocol	Confidential
P5-PK-01-EXP	2.0, Approved	Page 10 of 98
P.1. 1. 01/2 0012500		

- 12. Subject or one of their family members ^a is employee of the investigational site or of any other contracted vendors involved in the study.
- 13. Subject has participated in another clinical study within 30 days prior to the Screening Visit.
- 14. Subject has been previously screened or enrolled in this study.
- 15. For women only: subject is pregnant (does not have negative pregnancy tests at Screening Visit and at Admission) or is breastfeeding.
- 16. For women of childbearing potential only ^b: subject does not agree to use an acceptable method of effective contraception ^c.
- 17. Use of estrogen-containing hormonal contraception or hormone replacement therapy.
- a. As defined by US Food and Drug Administration (FDA) guidance on Human Subject Protection (21 CFR 50.3(1), (m), 50.24(a)(6), (a)(7)(v), b)):
 "Family member" means among other things "parent", "spouse", "brothers, sisters, and spouses of brothers and sisters" and "any individual related by affinity...whose close association with the subject is equivalent of a family relationship"
- b. Women who are not of childbearing potential meet at least one of the following criteria:
 - Have undergone hysterectomy or bilateral tubal ligation,
 - Have primary ovarian insufficiency, or
 - Are medically confirmed to be post-menopausal (cessation of regular menses for at least 12 consecutive months with no alternative pathological or physiological cause).
- c. Intrauterine device, intrauterine system, barrier methods of contraception (condoms, occlusive caps) with spermicidal foam/gel/film/suppository, hormonal contraception without estrogens, vasectomized partner(s), or true abstinence (periodic abstinence and withdrawal are not effective methods) from Screening until the end of the Safety follow-up period.

Confidentiality Statement

Document ID: VV-TMF-00821

Investigational Products; Dose; and Mode of Administration:

The 4 variants of Nicotine pouch 1.0, Velo-NP and Zyn-NP will be provided by the Sponsor. The distribution will be controlled by the Investigator or a qualified and appropriately trained designee.

The following variants of NP 1.0, Velo-NP and Zyn-NP will be investigated:

Test Produc	t
-------------	---

Name	Name in this study	Nicotine per pouch	рН	Moisture	Flavor
NP-1	NP-1	8.4 mg	8.0	30	Cool mint
NP-2	NP-2	8.4 mg	9.0	30	Cool mint
NP-3	NP-3	3.6 mg	8.0	15	Cool mint
NP-4	NP-4	3.6 mg	8.0	30	Cool mint

Comparator Product

Name	Name in this study	Nicotine per pouch	Flavor
Velo® Ice Cool	Velo-NP	10 mg	Cool mint
Zyn® Cool Mint Mini Dry	Zyn-NP	3 mg	Cool mint

Duration of Study:

The entire study per subject will between 8 and 27 days. This will include a screening period of up to 21 days prior to Admission (Day -22 to Day -2), 3 days of confinement (after enrollment on Day -1 to discharge on Day 3, (3 overnight stays), and a 3-day Safety follow-up period (from time of Discharge at Day 4 to Day 6). The end of the study (EOS) for a subject is defined as the end of the Safety follow-up period. The end of the whole study corresponds to the individual EOS of the last subject.

Confidentiality Statement

Statistical Methods:

Demographics and baseline characteristics will be summarized for the safety population and PK populations.

PK, PD, and extent of use parameters will be summarized in the PK population, by product and for all the planned timepoints.

Nicotine PK parameters will be derived from Background-Corrected Plasma Nicotine Concentrations using NCA.

Safety data will be listed and tabulated in the Safety population. Safety variables collected during exposure period will also be reported by sequence. All data will be presented in listings, ordered by randomized sequence, subject, and time point unless otherwise specified.

All endpoints will be summarized with descriptive statistics including number of subjects (n), number and percent of subjects with missing data, arithmetic means, and standard deviations (mean and SD), median, first and third quartiles, minimum and maximum, and change from baseline.

For log normally distributed endpoints, geometric mean, geometric CV, confidence interval of the geometric mean, and percent change from baseline will be presented in addition.

Categorical variables will be summarized by frequency statistics (number and percentage).

For endpoints relating to sampling times (e.g., T_{max}), only median, first and third quartiles, and minimum and maximum will be presented.

A mixed model analysis of variance (ANOVA) will be conducted on C_{max} , AUC_{0-5min}, AUC_{0-10min}, AUC_{0-15min}, AUC_{0-20min}, AUC_{0-25min}, AUC_{0-30min}, AUC_{0-35min}, AUC_{0-40min}, AUC_{0-1h}, AUC_{0-3h}, AUC_{0-6h}, and AUC_{0-infinity} endpoints in the natural logarithmic scale. The results of this analysis will be presented in terms of geometric least square mean ratios and 95% confidence intervals (95% CI).

The analysis of T_{max} will be conducted using non-parametric tests and Hodges-Lehmann estimates of median difference with its derived 95% CI.

Sample Size and Evaluation:

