2.3.2 Anticipated Foreseeable Risks due to Study Procedures

The risk of scheduled procedures in the present study (e.g., blood samples) are deemed to be on par with procedures routinely performed during normal or extended health examinations by the subject's healthcare professional. The total volume of blood to be drawn is approximately 340 mL and does not exceed the levels for a standard blood donation. The risks related to blood sampling include for example: excessive bleeding, fainting, hematoma, paresthesia or infection, and those related to the total amount of blood taken over a period of time such as weakness, dizziness or anemia.

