7.7.1 Blood Samples

Blood samples will be drawn by qualified and trained site personnel and according to the standard operating procedures (SOPs) at the investigational site.

Confidentiality Statement

Philip Morris Products S.A.	Clinical Study Protocol	Confidential
P5-PK-01-EXP	2.0, Approved	Page 54 of 98

Since the test for nicotine concentration is highly sensitive, precautions should be taken during blood sampling and processing to prevent the contamination of samples with environmental nicotine.

In total, approximately 340 mL of blood will be collected for this study including samples for determination of plasma nicotine concentrations (approximately 296 mL), CYP2A6 activity (5 mL), and safety laboratory including serology (approximately 37.5 mL). This calculation is based on an individual volume of each sample of 4.0 mL for nicotine PK, 5.0 mL for CYP2A6 analysis, 12.5 mL per safety laboratory assessments, including serology. The total volume of blood drawn will not exceed the levels for a standard blood donation.

Details on the procedures for collection, labeling, handling and shipment of samples are described in the SHM/ laboratory manual.

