9.1 Screening Visit (Day -22 to Day -2)

The Screening Visit will be performed within 21 days prior to enrollment at Admission (Day -1). Screening procedures must not be started before study information is given to the subject and the consent form signed by the subjects. Then, screening procedures can be performed in the order deemed most practical. While it is recommended to complete as many screening procedures as possible in one day, it is permissible to complete those over more than one day. Smoking is allowed at the Screening Visit at the discretion of the investigational site.

Screening activities are listed in Table 4.

Time	Blood Sample	Procedures	Additional Information
Prior to any study procedure		Informed consent process and signature of ICF	
During the visit		Information on the risks of smoking/advice on smoking cessation and debriefing on NP 1.0	Section 7.2
		Nicotine/Tobacco product use history	Section 7.8.2
		FTND questionnaire	Section 7.8.1
		Demographics data	Section 7.4.1
		Medical history/ concomitant diseases	Section 7.4.2
		Prior (within 4 weeks prior to the Screening Visit) and concomitant medication	Section
		Physical examination	Section 7.4.3
		Body height, weight and calculated BMI	Section 7.4.4
	C		

Table 4Time Schedule – Screening Visit

Confidentiality Statement

Philip Morris Products S.A.

Clinical Study Protocol 2.0, Approved Confidential Page 63 of 98

Related to QMS-0017588

Document ID: VV-TMF-00821

Time	Blood Sample	Procedures	Additional Information
		Vital signs	Section 7.4.5.
		ECG	Section 7.4.7
		Spirometry	Section 7.4.6
	Х	Clinical laboratory parameters (hematology, clinical chemistry)	Section 7.6.1
		Collection of spot urine for:	
		Urine analysis safety panel	Section 7.6.1
		 Urine drug test including testing for alcohol 	Section 7.6.3
		Urine cotinine test	Section 7.6.4
		 Urine pregnancy test (all female subjects) 	Section 7.6.5
	Х	Serology	Section 7.6.2
		Review of inclusion/exclusion criteria based on all relevant assessments	
		AE/SAE recording	

Abbreviations: AE = Adverse event; BMI = Body mass index; ECG = Electrocardiogram; HIV = Human immunodeficiency virus; SAE = Serious adverse event.

If the inclusion and exclusion criteria are met, the investigational site staff will contact the subject to arrange Day -1 visit at site.

Confidentiality Statement

Confidential Page 64 of 98

Related to QMS-0017588

Document ID: VV-TMF-00821

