a. Prior to enrollment at Admission on Day -1, the following inclusion and exclusion criteria will be re-checked: Inclusion Criteria: (4) Subject has smoked ≥ 10 commercially available cigarettes per day for 4 weeks prior to Screening Visit and Admission. Smoking status will be verified based on a urinary cotinine test (cotinine ≥ 500 ng/mL), (5) Subject does not plan to quit smoking or using other nicotine/tobacco-containing products in the next 3 months. Exclusion criteria: (10) Subject has a positive urine drug including alcohol test, (15) For women only: subject is pregnant (does not have negative pregnancy tests at Screening Visit and Admission) or is breastfeeding, (16) For women of childbearing potential only: subject does not agree to use an acceptable method of effective contraception, (17) Use of estrogen-containing hormonal contraception or hormone replacement therapy.

Confidentiality Statement

Philip Morris Products S.A.	Clinical Study Protocol	Confidential
P5-PK-01-EXP	2.0, Approved	Page 97 of 98

Document ID: VV-TMF-00821

The following eligibility criteria will only be checked at Admission: (7) Subject has received medication within 14 days or within 5 half-lives of the drug prior to Admission, whichever is longer, which has an impact on CYP2A6 activity.

- b. Sex, date of birth/age, race and ethnicity.
- c. Concomitant disease status.
- d. All medication taken within 4 weeks prior to the Screening Visit will be documented. Prior medication which has an impact on CYP2A6 activity taken within 14 days or within 5 half-lives of the drug (whichever is longer) prior to Day -1 is an exclusion criterion.
- e. Systolic and diastolic blood pressure, pulse rate and respiratory rate. On Day 1 to Day 3 in the morning, vital signs will be assessed prior to T_{0M} .
- f. At Screening an ECG will be performed after signed ICF and at least 1 hour after smoking cigarettes, on Day -1 an ECG will be performed prior to enrollment, on Day 3 an ECG will be performed 60 minutes \pm 10 minutes after T₀.
- g. Blood samples should be taken in the morning of the Screening visit, Admission (Day -1) and Discharge (Day 3) or at Early termination. Subjects should have fasted for at least 10 hours prior to safety laboratory assessments except at the Screening visit and Early termination where non-fasting samples will be used.

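### Exclusions 5 (blood donation or receipt) and 13 (another clinical study) stop at Screening and are not re-checked at Admission, leaving up to 21 days uncovered before about 326 mL is drawn.

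*Protocol*

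**What the plan says.** Exclusion 5 is worded "Subject has donated or received whole blood or blood products within 30 days prior to Screening Visit" and exclusion 13 "Subject has participated in another clinical study within 30 days prior to the Screening Visit". The synopsis, Protocol 5.1.2 and SAP 3.2.2 agree on both. In the two tables each criterion has a mark under Screening and none under Admission.

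Appendix A note a governs what is looked at again: "Prior to enrollment at Admission on Day -1, the following inclusion and exclusion criteria will be re-checked". The list that follows has inclusion 4 and 5 and exclusions 10, 15, 16 and 17. The note then adds one item reserved for that visit: "The following eligibility criteria will only be checked at Admission: (7) Subject has received medication within 14 days". Exclusions 5 and 13 appear in neither list.

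Protocol 9.1 allows Screening at any time from Day -22 to Day -2, with enrollment on Day -1. On the blood taken by the study, Protocol 2.3.2 states: "The total volume of blood to be drawn is approximately 340 mL and does not exceed the levels for a standard blood donation". The same section names weakness, dizziness and anemia among the risks of the total amount taken over time.

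**The concern.** Exclusion 5 keeps recently bled subjects out of a study with heavy sampling. As written, it removes someone who donated 30 days before Screening but not someone who donated the day before Admission, although the second is closer to the study's own draws. Exclusion 13 has the same gap for another study.

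Elsewhere the protocol allows for status changing between the two visits. Exclusion 7 counts back from Admission, inclusion 4 covers the weeks before both visits, and exclusions 10 and 15 to 17 are checked twice. Exclusions 5 and 13 do not get this treatment.

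What is at stake is subject protection. For donation, it is the cumulative blood loss. For another study, NP 1.0 has not been tested in humans (Protocol 2.1.2), and subjects come partly from a volunteer database used to fill successive studies (Protocol 13.2), so overlapping participation is plausible.

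**Working it through.** **Inputs.**
- Volumes per sample (Protocol 7.7.1): "4.0 mL for nicotine PK, 5.0 mL for CYP2A6 analysis, 12.5 mL per safety laboratory assessments, including serology".
- PK samples (Appendix A note l; SAP Table 6.1): 24 per day on Days 1 to 3, plus 2 extra on Day 2.
- Safety laboratory draws (Appendix A note g): Screening, Day -1 and Day 3.
- CYP2A6 (Appendix A note i): one sample, on Day -1.

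**Reproducing the plan's total.**
- PK: 3 × 24 + 2 = 74 samples; 74 × 4.0 = 296 mL, as stated.
- CYP2A6: 5 mL.
- Safety laboratory: 3 × 12.5 = 37.5 mL, as stated.
- Total: 296 + 5 + 37.5 = 338.5 mL, against a stated figure of about 340 mL. It reproduces.

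Reading the schedule as 12 PK samples per day would give (3 × 12 + 2) × 4.0 = 152 mL of PK blood and 152 + 5 + 37.5 = 194.5 mL in total. That does not match, so 24 per day is the operative count.

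**Volume from Admission onward.**
- Day -1: 12.5 + 5 = 17.5 mL.
- Day 1: 24 × 4.0 = 96 mL.
- Day 2: 26 × 4.0 = 104 mL.
- Day 3: 96 + 12.5 = 108.5 mL.
- Sum: 17.5 + 96 + 104 + 108.5 = 326 mL.

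If serology makes the Screening draw larger than the other two safety draws, this figure falls slightly.

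**Length of the uncovered interval.** Screening on Day -22 and Admission on Day -1 gives 22 − 1 = 21 days; Screening on Day -2 gives 2 − 1 = 1 day. Measured from Admission, the 30-day window covers days 21 to 51 back in the first case and days 1 to 31 back in the second. What it leaves out is always the most recent stretch.

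**Combined loss after a donation in the interval.** The documents give no volume for a standard donation. Protocol 2.3.2 says the study total of about 340 mL does not exceed one, so I assume a whole-blood donation is at least about 340 mL. Then 340 + 326 = 666 mL, or roughly 665 mL or more. Adding the 12.5 mL Screening draw gives 666 + 12.5 = 678.5 mL. Day -22 to Day 3, with no Day 0, spans 22 + 3 = 25 calendar days.

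**Does other text close the gap?** The restrictions in Protocol 6.6 cover nicotine, diet and exercise. The discontinuation reasons in 5.2 and the deviations named in 11.1.2 mention neither event. The Admission procedures in Table 5 include no question on donation or other studies.

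**The case against.** The strongest reply is that Admission is not a formality. Table 5 places hematology, clinical chemistry, vital signs, physical examination, ECG and concomitant medication and disease status before enrollment on Day -1. Protocol 5.2 requires discontinuation for a condition, including a laboratory change, that the Investigator finds incompatible with participation, or when it is in the subject's best interest. The documents also agree with one another on this point, so there is no contradiction to resolve, and consent pages are not available, so instructions to subjects cannot be checked.

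That stands as mitigation and rules out four stronger readings that a reader might infer:

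- *Such a subject is automatically enrolled.* Not supported. The Day -1 checks and Investigator discretion may stop enrollment.
- *The hematology change endpoint is disturbed.* Not supported. Under SAP 8.7 the baseline is typically the Day -1 result, so a donation in the interval precedes it and lowers both values. The study's own sampling between the two laboratory draws, 5 + 96 + 104 = 205 mL, affects every subject.
- *Exposure from another study enters unseen.* Not supported. Medication from Screening onward must be documented (Protocol 6.7 and 7.4.2), and CYP2A6-active drugs exclude by reference to Admission.
- *The premise of Protocol 2.3.2 fails.* Not supported. It speaks only of this study's draw, which stays about 340 mL whatever came before; it says nothing about cumulative loss.

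The objection does not supply a rule on either event or a requirement to ask. Inclusion 6 and exclusion 3, the criteria that use examination and laboratory findings, are themselves marked for Screening only. Discretion operates only if the Investigator learns of the donation or the other study.

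**Conclusion.** The gap is real but modest. For 1 to 21 days before Admission, blood donation or receipt and participation in another study meet neither exclusion, and the safeguards that remain are indirect. In the donation case, a subject could lose roughly 665 mL or more across the donation and the draws from Day -1 to Day 3. That figure rests on the donation being whole blood of at least about 340 mL; exclusion 5 also covers blood products, for which it need not apply. How many subjects would be affected is unknown and probably few.

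This is a point of subject protection and of consistency in how eligibility is timed. It does not touch the PK analysis or the sample size. It rates as a cheap improvement.

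**What to change.** In the synopsis, Protocol 5.1.2 and SAP 3.2.2, define the window in both exclusions as *in the period from 30 days before the Screening Visit until Admission*. State both ends: a looser phrase such as *at any time up to Admission* could be read as excluding anyone who has ever donated or joined a study. Mark both criteria in the Admission column and add both to the re-check list in Appendix A note a. The same edit can correct the column heading in the two exclusion tables, which places Admission on Day -3 while the rest of the plan has it on Day -1.

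The cost is a wording amendment, two extra questions on Day -1 and an occasional late screen failure. No procedure, sample or analysis changes.
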